- d: Samples for serum chemistry will be obtained following a fast of at least 10 hours, however, in case of dropouts or rechecks, subjects may not have fasted for 8 hours before the serum chemistry sample is taken. FSH and HbA1c are only required at screening.
- e: AE's will be monitored throughout the study. Study Investigators will attempt to contact all subjects who received at least one dose of study drug (including subjects who terminate the study early) using their standard procedures on Days 7 and 21 (\pm 2 days) whilst on study drug and on Days 35 ± 2 and 42 ± 2 (Follow-up) to determine if any AE has occurred since the last study visit. A compliance assessment will be conducted as a part of the Day 7 and Day 21 contact. Subjects will enter daily log of symptoms as well as study drug intake in a diary for the days when direct communication is not done.
- f: To be performed within 24 hours prior to dosing.
- g: Baseline 24hr PK will only be conducted on study drug naïve individuals.
- h: Prior to dosing.
- i: Participants will return to NIH CC on Day 27 for scheduled events. Participants will be observed and examined one day post cessation of dosing, for any withdrawal effects. Administration of the final dose and 24 hour PK will occur following approximately 28 days dosing (not to exceed 30 days).
- j: Approximately 14 days (\pm 2 days) following cessation of S 48168 (ARM210), participants will have follow-up safety laboratory tests.

Abbreviations: Admin = Administration, AE = Adverse event(s), C-I = Check-in, Chem = Chemistry, CYP = Cytochrome P450, FU = Follow-up, HIV = Human immunodeficiency virus, NIH CC = National Institutes of Health Clinical Center, PI = Principal Investigator, PK = Pharmacokinetics.

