In *mdx* mice, S 48168 (ARM210) was administered daily for 3 or 4 weeks in drinking water (*ad lib.*). This treatment was shown to have a beneficial effect: (i) on *in vivo* muscular function (*i.e.*, significant improvement of voluntary wheel activity at 10 and 50 mg/kg/day after 3 weeks of treatment, no decline in treadmill exhaustion test performance compared to vehicle-treated mice); (ii) on *in vivo* muscle force (*i.e.*, improvement of forelimb grip strength); and (iii) on *ex vivo* Extensor Digitorum Longus (EDL) specific force (3-week treatment) and diaphragm specific tetanic force at 50 mg/kg/day (4-week treatment) (Capogrosso et al., 2018). Two *in*

vitro parameters of intracellular Ca²⁺ homeostasis (*i.e.*, mechanical threshold and resting cytosolic Ca²⁺ level) were improved by a 4-week treatment of S 48168 (ARM210) at 50 mg/kg/day. [REDACTED]

Pharmacokinetics

After single oral administration in young healthy males of 20, 40, 80, 160, 240 and 400 mg of S 48168 (ARM210), rapid absorption was observed, after a lag time consistent with the GR properties of the tablet administered. There was no evidence of non-linearity with the dose. After 14-days of repeated once daily oral administrations of 20 mg of S 48168 (ARM210), the Cmax was reached with a median Tmax between 3 and 3.5 hours. Steady-state was attained after 3-7 days of daily treatment with S 48168 (ARM210). After 14-days of repeated administration of 20, 60, 120 and 240 mg of S 48168 (ARM210), accumulation ratios are around 1.5-1.8 for Cmax and AUC24, consistent with the half-life (20 hours) of S 48168 (ARM210) and its dose regimen.

The effect of food on the absorption of S 48168 (ARM210) has been tested in a three-period crossover study, comparing fasted with administration with a high fat breakfast, and with administration of a light breakfast [REDACTED]. The results showed that there is minimal effect on the exposure of S 48168 (ARM210) when administered with food when compared to fasted. The inclusion of food can delay the Tmax and blunt the Cmax so when PK is to be measured in the trial, S 48168 (ARM210) should be given fasted. However, on all other days S 48168 (ARM210) can be given without regard to food, *i.e.* fasted or with food.

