The PK profile of the 240 mg dose at steady state in healthy volunteers shows a slow decline over several days at the end of drug administration (Figure 2). This gradual decline in exposure reduces the risk of a sudden effect at the end of the dosing period due to withdrawal.

[figure not shown]

Figure 2. PK profile of S 48168 (ARM210) at day 1 and day 14 in healthy volunteers dosed at 240mg/day.

Modification of the Dose and/or Dosing Regimen

This protocol is written with some flexibility to accommodate the inherent dynamic nature of early clinical trials. Modifications to the dose and dosing regimen currently outlined below may be required to achieve the scientific goals of the trial objectives and/or to ensure appropriate safety monitoring of the trial subjects.

As such, lowering the currently outlined dose may be permitted based on newly available data, but the dose may not exceed 200 mg per day.

- Decrease in the dose of the trial drug administered during the study

The current top dose of \leq 200 mg/day (10 X 20 mg tablets) is not expected to exceed the Cmax limit of 35 ug/ml (projected mean from healthy volunteer data of 28 ug/ml). However if PK monitoring reveals that the limit could be exceeded, then 180 mg/day will be given (9 X 20 mg tablets). This dose would be projected to have a Cmax of 25.75 ug/ml.

- Decrease in the duration of trial drug administration (e.g., number of days) in the study
- Addition of a pharmacokinetic data review

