There may be some psychological distress associated with recalling adverse events. A clinician will conduct remote TEAE reporting data collection and be available for any questions the participant may have relating to their responses. Participants local to the study site will have the option of completing TEAE assessments at the NIH.

Post-study follow-up blood draw

The risks associated with phlebotomy (detailed above) apply. A study investigator will contact participants by telephone to remind them of upcoming, scheduled local phlebotomy appointments.

Administration of study drug

As this is a phase 1 study, and the first time S 48168 will be administered to a patient population, we consider administration of study drug to be greater than minimal risk. To date however, data are available for a total of 107 adult healthy male Caucasian participants aged 18-45 years that participated in Phase 1 clinical studies. Of these participants, 90 were exposed to S 48168 (ARM210) treatment. S 48168 (ARM210) has been safe and well-tolerated in single doses up to 240 mg and in 14 days of multiple dosing up to 240 mg daily (un-blind data), and in single dose of 400 mg and 14 days of multiple dosing of 240 mg daily (blinded data). No serious AEs were reported. There were no clinically significant, dose dependent changes in vital signs, physical examination, laboratory data, ECG and telemetric data.

Risk to the participant from study drug administration will be minimized through 24h inpatient monitoring following administration of the first dose and AE monitoring scheduled throughout the intervention phase as well as 1 day, 7 ± 2 days, and 14 ± 2 days post-intervention. As a precaution, all participants will be provided with a malignant hyperthermia alert bracelet and asked to wear this throughout the study and two-week follow-up.

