11.6 Selection of Study Population

11.6.1 Inclusion Criteria

Patients must meet all the following conditions to be eligible for enrollment into the study:

1. Adult males and females, 18 – 65 years of age, inclusive, at screening.
2. Body mass index (BMI) ≥ 18.0 and $\leq 36.0 \text{ kg/m}^2$ at screening.

3. Confirmed genetic diagnosis of *RYR1*-RM and supporting clinical phenotype with demonstrable deficits on at least one of the baseline study assessments.
4. Evidence of functional deficit (defined by MFM-32 \leq 80% maximum score) or demonstrable deficits in at least one of the baseline muscle/motor function assessments.
5. Ambulatory. Able to walk ten meters (with or without assistance e.g. with a cane).
6. Must have a CYP2C8 extensive or intermediate metabolizer genotype.
7. Daily use of medicines and dietary supplements need to be approved by the PI and Sponsor, or a drug/supplement-dependent wash-out prior to inclusion.
8. For male subjects: is sterile or agrees to use an appropriate method of contraception, including a condom with spermicide, from study drug administration on the first day of dosing until 5 half-lives plus 90 days (approximately 94 days) after the last dose of study drug administration. No restrictions are required for a vasectomized male subject provided the subject is at least 1-year post-bilateral vasectomy procedure prior to study drug administration on first day of the first dose. A male subject whose vasectomy procedure was performed less than 1 year prior to study drug administration on the first day of dosing must follow the same restrictions as a non-vasectomized male. Appropriate documentation of surgical procedure should be provided.
9. For male subjects: agrees to not donate sperm from study drug administration on the first day of dosing until 5 half-lives plus 90 days (approximately 94 days) after the last dose of study drug.
10. For female subjects of childbearing potential: uses one of the following highly effective birth control methods (from the first dose until 5 half-lives plus 90 days (approximately 94 days)):
 - Prescribed hormonal oral contraceptives, vaginal ring, or transdermal patch.
 - Intrauterine device (IUD).
 - Intrauterine hormone-releasing system (IUS).
 - Depot/implantable hormone (e.g., Depo-provera®, Implanon).
 - Bilateral tubal occlusion/ligation.
 - Sexual abstinence:
 - Refraining from heterosexual intercourse during the entire period of risk associated with the study requirements.

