even in this short study, there may be improvement in muscle function and strength with approximately 28 days (not to exceed 30 days) of dosing with S 48168 (ARM210). Although there are no mechanistic reasons to assume that removal of the drug after the proposed dosing period would have any consequences other than a return to baseline function, post-dose monitoring has been included in the study. These measures include observation and examination after 24 hours off drug, as well as remote TEAE monitoring and a blood draw for safety labs on day 35 ± 2 days, approximately one week off drug and a remote TEAE assessment on day 42 ± 2 days, approximately two weeks off drug. A study investigator will contact participants to remind them of upcoming, scheduled local phlebotomy appointments. Participants local to the study site will have the option of completing AE assessments and safety laboratory tests at the NIH.

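### The one examination labelled for withdrawal effects falls at the ordinary daily trough; the diary through washout is unclear, and the SAP does not separate washout-onset events

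*Protocol*

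**What the plan says.** **Post-dose checks.** Footnote i of the flow chart (Protocol, Section 7) reads: "Participants will be observed and examined one day post cessation of dosing, for any withdrawal effects". Section 11.1 repeats this and adds that no such effects are expected. Section 12.10 gives a wider package: "These measures include observation and examination after 24 hours off drug, as well as remote TEAE monitoring and a blood draw for safety labs" at Day 35 ± 2, then an assessment at Day 42 ± 2. Section 11.2 lists AE monitoring at "1 day, 7 ± 2 days, and 14 ± 2 days post-intervention". Under footnote e, the Day 35 and Day 42 contacts ask about any AE since the last study visit.

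**Pharmacokinetics.** Section 9.4 describes accumulation as "consistent with the half-life (20 hours) of S 48168 (ARM210) and its dose regimen". Section 9.5 says that the steady-state profile at 240 mg in healthy volunteers "shows a slow decline over several days at the end of drug administration", and uses this to argue that a sudden withdrawal effect is less likely.

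**Diary.** Footnote e asks for a daily record of symptoms and drug intake on days without direct contact. Section 11.1 says that the diary captures symptoms between remote TEAE assessments. Neither ends the diary at the last dose. The diary row of the flow chart has no mark after Days 23-26.

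**Analysis.** SAP Section 6.3 defines a TEAE as an AE that starts or worsens at or after dosing and attributes it to a treatment by onset date and time. SAP Tables 14.3.1.1-14.3.1.4 are laid out by treatment, with no split between time on drug and time after the last dose.

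**The concern.** An examination for withdrawal is informative only if exposure has dropped below what the participant is used to. At 24 h after a once-daily dose it has not: the participant has been at this level every morning since reaching steady state. A clean examination then says little about stopping the drug.

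The protocol's own argument in Section 9.5 places the decline over the following days. No telephone call or visit is scheduled during most of that decline. If the diary also stops with dosing, brief or mild symptoms in that period depend on recall some days later, whereas symptoms on drug were logged daily. Even when such events are captured, the planned tables pool them with on-drug events, so a reader of the study report could not see them as a group without going through the listings. Safety and tolerability is the primary objective, and Section 12.10 says that post-dose monitoring was included because of drug removal.

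**Working it through.** **Inputs.** Half-life 20 h, once-daily dosing (interval 24 h) and median Tmax 3-3.5 h (Protocol 9.4). Accumulation: "accumulation ratios are around 1.5-1.8 for Cmax and AUC24" (9.4). The contraception period runs "until 5 half-lives plus 90 days (approximately 94 days) after the last dose of study drug administration" (11.6.1). Contacts at Day 35 ± 2 and Day 42 ± 2 (Section 7, footnote e). Target of about 8-20 completers (11.1). I assume mono-exponential decline and a patient half-life like that of healthy volunteers; Section 9.5 says that the patient profiles seen so far are consistent with the volunteer studies.

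**Step 1: reproduce the plan's figures.**
- Accumulation = 1/(1 − 2^(−24/20)) = 1.77, inside 1.5-1.8. Inverting that range gives half-lives of 15.1 to 20.5 h.
- Five half-lives = 5 × 20/24 = 4.17 days; plus 90 = 94.2 days, matching the stated 94.

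**Step 2: exposure at the 24 h examination.** Taking Tmax as 3.25 h, the level relative to Cmax is 2^(−(24 − 3.25)/20) = 0.487, about 49%. This is the normal pre-dose trough.

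**Step 3: decline after that.** Level as a percentage of the usual trough = 100 × 2^(−(t − 24)/half-life). The 15 h and 24 h columns are an assumed range; 24 h would imply accumulation of 2.0, above the stated range.

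| Hours after last dose | 15 h | 20 h | 24 h |
|---|---|---|---|
| 24 | 100 | 100 | 100 |
| 48 | 33 | 44 | 50 |
| 72 | 11 | 19 | 25 |
| 96 | 3.6 | 8 | 12.5 |
| 120 | 1.2 | 3.6 | 6.3 |
| 168 | 0.1 | 0.7 | 1.6 |

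Between 24 h and 120 h the participant loses about 96% of the usual trough level (100 − 3.6), or 94-99% over the assumed range.

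**Step 4: the next scheduled contact.** The Day 35 window is Day 33 to Day 37.
- Last dose on Day 28: 5 to 9 days off drug, when 3.6% to 0.1% of the trough level remains.
- Last dose on Day 30: 3 to 7 days off drug, when 19% to 0.7% remains.

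After a Day 28 last dose, even the earliest contact comes when almost all of the decline is over. After a Day 30 last dose, an early contact could fall within it.

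**Step 5: what the numbers can support.** With no events in n participants, the one-sided 95% upper bound on the event rate is 1 − 0.05^(1/n): 31% for n = 8 and 14% for n = 20.

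**The case against.** The 24 h examination is one of three post-dose checks. The Day 35 and Day 42 contacts look back to the previous visit, so AEs in the washout days are sought. Section 12.10.7.4 keeps AEs reportable through 28 days after each dose. Section 11.1 makes Day 42 an in-person visit with physical examination, safety labs and the functional battery. Footnote e and Section 11.1 can fairly be read as continuing the diary on days without contact. As extracted, the flow chart has no columns for Days 29-34, so a missing mark does not prove that the diary stops. All of this stands.

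A reader might therefore go too far in three ways.
- **That the washout is unmonitored.** It is not: it is covered by recall, and perhaps by the diary.
- **That a planned comparison of AEs on and off drug is biased.** No such comparison is planned. The AE comparison in SAP 6.3 is descriptive, against historical controls. Under-reporting through recall is plausible if the diary stops, but the documents do not allow it to be sized.
- **That the plan fails to show absence of withdrawal effects.** Withdrawal is neither an objective nor an endpoint, and Step 5 shows that no schedule could demonstrate absence in 8-20 open-label participants.

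The objection does not make the 24 h examination informative about withdrawal, settle where the diary ends, or let the tables show when events began relative to the last dose.

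**Conclusion.** The point holds in a limited form. The only examination labelled for withdrawal takes place at ordinary trough exposure and, on its own, says little. About 96% of that trough level is lost between 24 h and 120 h off drug, mostly before any scheduled live contact. This does not depend on the exact half-life within 15-24 h; it does rest on roughly mono-exponential decline in patients.

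Two gaps follow. The protocol's text and its flow chart do not agree on whether the diary covers those days, and the SAP tables pool washout-onset TEAEs with on-drug TEAEs. Neither threatens the primary endpoint as defined. They limit what the report can say about stopping the drug, and both can be corrected without a new visit.

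**What to change.** 1. **Diary.** State in the flow chart, footnote e and Section 11.1 that the existing daily symptom diary continues from the last dose through Day 42. While doing so, reconcile Sections 12.10 and 12.10.7.3, which still describe the Day 42 assessment as remote, with the Synopsis and Section 11.1, which make it in person.
2. **Tables.** In SAP 6.3 and Tables 14.3.1.1-14.3.1.4, show TEAEs with onset more than 24 h after the last dose separately from on-drug TEAEs. State how an AE with a missing onset date or time is placed. The final dose at the clinic has a recorded clock time (Protocol 11.8.1), so the cut-off is well defined for completers.
3. **Wording.** In footnote i, 11.1 and 12.10, describe the 24 h examination as an end-of-dosing-interval check. Base any statement on withdrawal effects on all data from 24 h after the last dose through Day 42. Starting only after five half-lives (about 4 days) would discard the decline itself.

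The cost is about two more weeks of an existing diary and one extra table split. Counts will be small, so the output is descriptive.

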8 ABBREVIATIONS

AE	Adverse event
ALT	Alanine aminotransferase
AST	Aspartate aminotransferase
AUC	Area under the concentration-time curve
AUC%extrap	Percent of AUC0-inf extrapolated
AUC0-t	Area under the concentration-time curve, from time 0 to the last observed non-zero concentration (t)
AUC0-inf	Area under the concentration-time curve, from time 0 extrapolated to infinity
AUCtau	The area under the concentration-time curve during a dosing interval (tau) at steady state
BCRP	breast cancer resistance protein
BMD	Becker Muscular Dystrophy
BMI	Body mass index
°C	Degrees Celsius
Ca ²⁺	Calcium ion(s)
CD	Clinical Director NINDS
CDM	Clinical Data Management
CFR	Code of Federal Regulations
cGMP	Current Good Manufacturing Practices
Cm	Centimeter
Cmax	Maximum observed concentration
Cmax,u	Maximum plasma unbound concentration
Cmin	Minimum concentration at steady state
CNS	Central nervous system
CRF	Case report form
Ctrough	Concentration observed at the end of the dosing interval
CV	Coefficient of variation
CYP	Cytochrome P450
D	Day
DICR	depolarization-induced Ca ²⁺ release

DMD	Duchenne Muscular Dystrophy
DSMB	Data and Safety Monitoring Board
ECC	Excitation-contraction coupling
ECG	Electrocardiogram
EDC	Electronic Data Capture
EDL	Extensor Digitorum Longus
FKBP12	12 kDa FK506-binding protein-Calstabin1
FDA	Food and Drug Administration
FEV ₁	Forced Expiratory Volume at 1 second
FIM	First-in-man
FWA	Federal Wide Assurance
G	Gram
GCP	Good Clinical Practice
GLP	Good Laboratory Practice
GR	Gastro-resistant
H	Hour
HBsAg	Hepatitis B surface antigen
HCV	Hepatitis C virus
HIV	Human immunodeficiency virus
HPLC-MS-MS	High performance liquid chromatography with tandem mass spectrometry
HRPP	Human Research Protection Program
IB	Investigator's Brochure
ICF	Informed Consent Form
ICH	International Council for Harmonisation
IND	Investigational New Drug
IRB	Institutional Review Board
K ₂ EDTA	Dipotassium ethylenediaminetetraacetic acid
Kel	Apparent terminal elimination rate constant
Kg	Kilogram
m ²	Meters squared
MedDRA®	Medical Dictionary for Regulatory Activities®
MFM	Motor Function Measure 32

miU	Milli-international units
Mg	Milligram
mL	Milliliter
mmHg	Millimeter of mercury
N	Sample size
NCA	Non-compartmental analysis
NIH	National Institute of Health
NIH CC	NIH Clinical Center
NINDS	National Institute of Neurological Disorders and Stroke
NMD	Neuromuscular diseases
No.	Number
NOEL	No observed effect level
Oz	Ounce
PD	Pharmacodynamics(s)
PFT	Pulmonary Function Tests
PI	Principal Investigator
PII	Personally identifiable information
PK	Pharmacokinetic(s)
QA	Quality assurance
RAAUC	Ratio of accumulation for AUC
RACmax	Ratio of accumulation for Cmax
RyR	Ryanodine receptor
RYR1	Ryanodine receptor isoform-1
RYR1-RM	RYR1-related myopathies
RYR2	Ryanodine receptor isoform-2
SAE	Serious adverse event
SAP	Statistical analysis plan
SAS	Statistical Analysis Plan
SERCA	Sarco/endoplasmic reticulum calcium-ATPase
SR	Sarcoplasmic reticulum
t ^{1/2}	Apparent terminal elimination half-life
Tau	Dosing interval

TE	Target engagement
TEAE	Treatment Emergent Adverse Events
Tlag	Lag time
Tmax	Time to reach maximum observed concentration
Tmin	Time to Cmin
ULN	Upper limit of normal
US	United States
USA	United States of America
VC	Vital capacity
WHO	World Health Organization

9 INTRODUCTION AND BACKGROUND

9.1 Introduction

Ryanodine receptor isoform 1-related congenital myopathies (*RYR1*-RM) are rare, slowly progressive neuromuscular diseases estimated to affect at least 1/90,000 pediatric individuals in the United States (Amburgey et al. 2011). Causative *RYR1* variants lead to a spectrum of *RYR1*-RM histopathological subtypes and clinical phenotypes. The most common clinical phenotype of *RYR1*-RM is a congenital myopathy. Affected individuals usually present with delayed motor milestones, proximal muscle weakness, impaired ambulation, and, in severe cases, scoliosis, ophthalmoplegia, and respiratory distress (Witherspoon and Meilleur, 2016). *RYR1*-RM may also cause rhabdomyolysis or atypical periodic paralysis and is associated with malignant hyperthermia. Histopathological subtypes include central core disease, multi-minicore disease, congenital fiber-type disproportion, centro-nuclear myopathy and core-rod myopathy. Although *RYR1*-RM have been associated with significant morbidities and early mortality, there remains no FDA-approved treatment.

Ryanodine receptor isoform-1 (RyR1) is the major skeletal muscle Ca^{2+} release channel. RyR1 is embedded within the sarcoplasmic reticulum (SR) membrane and is a principal component of skeletal muscle excitation-contraction coupling (ECC). Causative *RYR1* variants can have different effects on the RyR1 channel function. Some of these mutations result in chronic SR Ca^{2+} leak while others primarily impair ECC. Chronic Ca^{2+} leak into the sarcoplasm may result in increased mitochondrial-related oxidative stress, RyR1 channel oxidation, and cellular injury (Görlach et al. 2015).

